Doc id 05DF1910 Clinical Study Protocol 🚣 GALDERMA MA-42248

A Randomized, Evaluator-Blinded Study to Evaluate Facial Harmony and Subject Satisfaction Using Restylane Defyne in a Stepwise Treatment Approach

Study products: Restylane® Defyne™

Clinical trial number (CTN): 05DF1910

O-Med AB Sponsor:

[name]

[name] [contact] [contact]

Confidentiality Statement

This study protocol contains confidential information belonging to Q-Med AB. Except as may be otherwise agreed to in writing, by accepting or reviewing these materials, you agree to hold such information in confidence and neither disclose it to any third parties (except where required by applicable law) nor use it for any other purpose than in relation to the clinical study described herein.

	Title	Doe id
•	05DF1910 Clinical Study Protocol	
💑 GALDERMA		344 43340
		MA-42248

Investigators and Study Administrative Structure

Coordinating Investigator:	
Sponsor:	Q-Med AB [name] [name] [contact]
Senior Medical Expert:	PPD
PPD	PPD
PPD	PPD
Clinical Project Manager: Statistician:	PPD

[figure not shown]
Further details on all participating Investigators and the complete administrative structure of the study are found in the study files. Note that administrative changes are to be documented in the study files without requiring a clinical study protocol (CSP) amendment.

• • • • • • • • • • • • • • • • • • • •	Tale 05DF1910 Clinical Study Protocol	Doc id
GALDERMA		MA-42248

Synopsis

Clinical Study Title:	A Randomized, Evaluator-Blinded Study to Evaluate Facial Harmony and Subject Satisfaction Using Restylane Defyne in a Stepwise Treatment Approach	
Clinical Trial Number:	05DF1910	
Region(s) / Country(ies) Involved and Planned Number of Study Sites:	Region/Country(ies): South America and Europe No. of Study Centres: 2 - 4	
Total Number of Subjects (Planned):	Approximately 60 subjects will be enrolled (of which at least 20 males).	
Clinical Study Design:	This is a 12-week, randomized, multi-centre, evaluator-blinded, on- label, post-market study.	
	Approximately 60 subjects (of which at least 20 males) will be enrolled and randomized into two groups. Stratification for site and gender will be performed. Both groups will be stepwise treated in the chin and nasolabial folds (NLF)/marionette lines (ML). One group will start treatment in chin (at baseline), followed by treatment in NLFs and MLs at week 3. The other group will start treatment in NLFs and MLs at baseline, followed by treatment in chin at week 3. The two groups are referred to as down-up and top-down, respectively.	
	An optional touch-up will be provided at week 6 for all subjects and treatment areas that have not obtained optimal aesthetic improvement as agreed between subject and Investigator. Subjects will be followed until week 9.	
	Study assessments, such as questionnaires, must be completed before treatment if injection is planned at the visit (applicable for baseline, week 3 and week 6 [if touch-up will be performed]).	
Clinical Study Duration:	First subject first visit to last subject last visit will be approximately 24 weeks: 12 weeks enrolment 3 weeks screening 9 week follow up	
Effectiveness Objectives and Endpoints:	Objective To evaluate aesthetic improvement after treatment in chin and NLFs/MLs, respectively, and in combination. Endpoint and Treating Investigator assessment using the Global Aesthetic Improvement Scale (GAIS) at week 3, 6 and 9.	

Doc id 05DF1910 Clinical Study Protocol GALDERMA MA-42248

Title 05DF1910 Clinical Study Protocol Doc id 👶 GALDERMA MA-42248

	CCI
Safety Objectives and Endpoints:	To evaluate Adverse Events (AEs) collected throughout the study. Device deficiencies will be assessed at treatment visits.
Inclusion Criteria:	Subjects willing to comply with the requirements of the study and providing a signed written informed consent.
	Subjects willing to undergo augmentation and correction therapy in the studied indications
	 Subjects willing to abstain from any other facial plastic surgical or cosmetic procedures for the duration of the study (e.g., laser or chemical resurfacing, facelift, etc.).
	 Adult males or non-pregnant, non-breastfeeding females and women of non-child bearing potential over the age of 21.
	 Urinary pregnancy test must be negative for females of childbearing potential at screening and all injection visits.
	Definition of non-child bearing potential:
	Women of non-childbearing potential are defined as those who have no uterus, ligation of the fallopian tubes, or permanent cessation of ovarian function due to ovarian failure or surgical removal of the ovaries. Postmenopausal women must be amenorrheic for at least 12 months to be considered of non-childbearing potential.
	5. If the subject is a female of childbearing potential, she agrees to use an acceptable form of effective birth control for the duration of the study and is willing to take a urine pregnancy test at the screening/enrolment visit and prior to treatment. Acceptable forms of effective birth control include:
	 Barrier methods of contraception: Condom or Occlusive cap (diaphragm or cervical caps) with spermicidal foam/gel/film/cream/suppository;
	Bilateral tubal ligation;
	Combined oral contraceptives (oestrogen and)

Effective

	Title	Doc id
•	05DF1910 Clinical Study Protocol	
💑 GALDERMA		3.5.4. 433.40
		MA-42248

		progesterone), implanted or injectable contraceptives on a stable dose for at least 28 days prior to Day 1;
		 Hormonal or copper intra uterine device (IUD) inserted at least 28 days prior to Day 1;
		 Vasectomized partner for at least 3 months prior to screening;
		 Strict abstinence (at least one month prior to baseline and agrees to continue for the duration of the study or use acceptable form of birth control).
Exclusion Criteria:	1.	Known/previous allergy or hypersensitivity to any injectable hyaluronic acid (HA) gel or to gram-positive bacterial proteins.
	2.	History of allergy or hypersensitivity to lidocaine or other amide-type anaesthetics, or topical anaesthetics or nerve blocking agents (if such products are intended to be used for that subject).
	3.	Previous or present multiple allergies or severe allergies, such as manifested by anaphylaxis or angioedema, or family history of these conditions.
	4.	Previous use of any permanent (non-biodegradable) treatment, lifting threads, permanent implants or autologous fat below the level of the horizontal line from the lower orbital rim.
	5.	Previous use of any semi-permanent treatment (e.g., calcium hydroxylapatite or Poly-L-Lactic acid) below the level of the horizontal line from the lower orbital rim within 24 months of the baseline visit.
	6.	Previous use of any HA based or collagen based biodegradable facial tissue augmentation therapy below the level of the horizontal line from the lower orbital rim within 12 months of the baseline visit.
	7.	History of other facial treatment/procedure in the previous 6 months that in the Treating Investigator's opinion, would interfere with the study injections and/or study assessments or exposes the subject to undue risk by study participation, e.g.:
		 Resurfacing (laser, photo modulation, intense pulsed light [IPL] radio frequency, dermabrasion, needling, chemical peel or other ablative/non-ablative procedures (such as ultrasound and cryotherapy))
		 Mesotherapy
		 Lipolytic injections (e.g. deoxycholic acid or other lipolytic substances)
		 Botulinum toxin injections below the level of the horizontal line from the lower orbital rim
	8.	Previous facial surgery, within 12 months, below the level of the horizontal line from the lower orbital rim.

Doc id 05DF1910 Clinical Study Protocol 🚣 GALDERMA MA-42248

- History of cancer or previous radiation near or on the area to be treated.
- 10. Presence of any disease or lesions near or on the area to be treated, e.g.:
 - · Inflammation, active or chronic infection (e.g., in mouth, head and neck region)
 - · Perioral dermatitis, active herpes simplex or herpes zoster lesions, or outbreak within 4 weeks from baseline, or history of four outbreaks, or more, during the last year.
 - Scars or deformities
 - Cancer, or precancer such as actinic keratosis or actinic cheilitis
- 11. Presence of tattoo, piercing, beard or facial hair, which, in the Treating Investigator's opinion, would interfere with the study injections and/or study assessment.
- 12. Presence of a dental, oral, or facial condition which, in the Treating Investigator's opinion, would interfere with the study injections and/or study assessment, e.g. has dentures or any device covering all or part of the upper palate, and/or severe malocclusion or dentofacial or maxillofacial deformities.
- 13. An underlying known disease, a surgical or medical condition that would expose the subject to undue risk, e.g. active hepatitis, autoimmune disease, history of bleeding disorders, connective tissue diseases such as rheumatoid arthritis, systemic lupus erythematosus, polymyositis, dermatomyositis, scleroderma.
- 14. Use of concomitant medication that have the potential to prolong bleeding times such as anticoagulants or inhibitors of platelet aggregation (e.g. aspirin [except low dose aspirin] or other non-steroidal anti-inflammatory drugs [NSAIDs], Omega 3 or Vitamin E), within 14 days prior to injection. Omega 3 and Vitamin E are acceptable only as part of a standard multivitamin formulation.
- 15. Treatment with chemotherapy, immunosuppressive agents, immunomodulatory therapy (e.g. monoclonal antibodies), systemic corticosteriods (inhaled corticosteroids are allowed) within 3 months prior to Baseline visit.
- Use of topical facial corticosteroids or prescription retinoids (below the level of the horizontal line from the lower orbital rim) within 1 month of the Baseline visit or systemic retinoid treatment within 6 months of the Baseline visit.
- Presence of any condition, which in the opinion of the Treating Investigator makes the subject unable to complete the study per protocol, e.g.
 - Subjects not likely to avoid other prohibited facial cosmetic treatments

ı		Title	Doc id
1		05DF1910 Clinical Study Protocol	
1	💑 GALDERMA	obbi 1710 Chinem Study 1100001	
1			MA-42248
1			
ı			

	Subjects not likely to complete the study because of other commitments
	 Subjects anticipated to be unavailable for visits, incapable of understanding the investigational assessments or having unrealistic expectations of treatment result
	 Subjects who have a concomitant condition (e.g. acute viral or bacterial infection with fever) that might confuse or confound study treatments or assessments
	 Participation in any interventional clinical study within 30 days of screening.
	19. Study site personnel, close relatives of the study site personnel (e.g., parents, children, siblings, or spouse), employees, or close relatives of employees at the Sponsor Company.
Investigational	Restylane Defyne
Product:	Cross-linked hyaluronic acid 20 mg/mL
	Lidocaine hydrochloride 3 mg/mL
	Phosphate buffered saline pH 7 qs ad 1 mL
	The syringe is packaged with two 27 Gauge (G) x ½" Ultra-Thin Wall (UTW) needles.
	At each treatment session, a maximum of 2 mL per treatment site is recommended per European Union (EU) label.
	Depending on the area to be treated and the tissue support, the product should be injected in the mid to deep dermis, subcutis or supraperiostic zone.
Treatment regimen:	Subjects randomized to down-up treatment (n=30 of which at least 10 males):
	Baseline - The chin and surrounding area to be treated with up to 2 mL of Restylane Defyne per treatment site with a maximum of 4 mL in total.
	Week 3 – NLFs and MLs to be treated with up to 2 mL/line per NLF and up to 2 mL per ML of Restylane Defyne
	Week 6 - Optional touch-up in any of the treated areas that have not obtained optimal aesthetic improvement. Up to 2 mL per facial half is recommended for NLF and MLs, and a total of 2 mL in the chin and surrounding area.
	Subjects randomized to top-down treatment (n=30 of which at least 10 males):
	Baseline – NLFs and MLs to be treated with up to 2 mL per NLF and up to 2 mL per ML of Restylane Defyne
	Week 3 – The chin and surrounding area to be treated with up to 2 mL of Restylane Defyne per treatment site, with a maximum of 4 mL in total.
	Week 6 – Optional touch-up in any of the treated areas that have not obtained optimal aesthetic improvement. Up to 2 mL per facial half is recommended for NLF and ML, and a total of 2 mL in the chin and surrounding area.

Blinded Evaluation:	Sufficient amount of study product should be injected to achieve optimal correction as agreed between the Treating Investigator and Treating Investigator. Investigator.		
Statistical Method:	CCI		
Sample Size:	The sample size of approximately 60 subjects (30 per treatment group) is not based on a statistical calculation. The selected number of subjects is regarded as sufficient for an evaluation of effectiveness and safety of the two treatment approaches when treating the chin, NLFs and MLs with Restylane Defyne.		

Tale 05DF1910 Clinical Study Protocol 👶 GALDERMA MA-42248

Abbreviations and Definitions of Terms

Abbreviation/Term	Definition
AE	Adverse event
CA	Competent Authority
CE	French: Conformité Européenne
CFR	Code of Federal Regulations
Coordinating Investigator	Investigator who is appointed by the Sponsor to coordinate work in a multicentre study
CRO	Contract research organization
CSP	Clinical study protocol
CTA	Clinical trial agreement
CTN	Clinical trial number
CV	Curriculum vitae
Device deficiency	Inadequacy of a medical device with respect to its identity, quality, durability, reliability, safety or performance (includes malfunctions, use errors, and inadequate labelling)
DMP	Data management plan
eCRF	Electronic case report form
EU	European Union
G	Gauge
GAIS	Global aesthetic improvement scale
GCP	Good clinical practice
GDPR	General Data Protection Regulation
HA	Hyaluronic acid
ICF	Informed Consent Form
ICH	International Conference on Harmonisation
IEC	Independent ethics committee
IFU	Instructions for use
IUD	Intra uterine device
Institution	Any public or private entity or agency or medical or dental facility where a clinical study is conducted.
Investigator	The Principal Investigator (PI) or other qualified person, i.e. sub-Investigator, designated and supervised by the PI at a study site to perform critical study-related procedures or to make important study-related decisions as specified on the signature and delegation log
Investigator file	Essential documents relating to a clinical study as defined in applicable GCP guidance document and maintained by the Investigator.

	Title	Doc id
👶 GALDERMA	05DF1910 Clinical Study Protocol	
		MA-42248

Abbreviation/Term	Definition
IPL	Intense Pulsed Light
IPR	Independent Photographic Reviewer
ISO	International Organization for Standardization
MDR	Medical Devices Regulation
MITT	Modified intention-to-treat
ML	Marionette lines
MedDRA	Medical dictionary for regulatory activities
NLF	Nasolabial fold
NSAID	Non-steroidal anti-inflammatory drug
OBT	Optimal Balance Technology
PI	Principal Investigator; qualified person responsible for conducting the study at a study site
PT	Preferred term
SAE	Serious adverse event
SDV	Source data verification
SOC	System organ class
Sponsor file	Essential documents relating to a clinical study as defined in applicable GCP guidance document and maintained by the Sponsor.
Study files	The Investigator file and the Sponsor file
Study products	The investigational product and the reference product under study
Study site	Institution or site where the study is carried out
Touch-up	Repeated injection to be performed after treatment, if necessary to achieve optimal correction
U-HCG	Urinary human chorionic gonadotropin
UTW	Ultra-Thin Wall
WHO	World Health Organization

Lucie				
05DF1910	Clinical	Study	Proto	col

Doc id

MA-42248

Tab	le of	Cont	tents
-----	-------	------	-------

INVE	NVESTIGATORS AND STUDY ADMINISTRATIVE STRUCTURE	
SYNO	SYNOPSIS	
ABBR	REVIATIONS AND DEFINITIONS OF TERMS	10
LIST	OF TABLES	15
LIST	OF FIGURES	15
LIST	OF APPENDICES	15
1. H	ETHICAL CONSIDERATIONS	16
1.1	Statement of ethical compliance	16
1.2	Application to independent ethics committee	16
2. H	BACKGROUND INFORMATION	17
2.1	Indication and population description	17
2.2	Study Product Profile	17
2.2.1	Investigational product description	17
2.3	Study rationale and justification for design	18
2.4	Risks and benefits	18

1.1 Statement of ethical compliance

The study shall be conducted in compliance with the clinical trial agreement (CTA), CSP, good clinical practice (GCP), and applicable regional or national regulations. The study shall be conducted in accordance with the ethical principles that have their origin in the Declaration of Helsinki (1964, and its amendments in force at the initiation of the study) (Appendix 1).

The study shall follow the international standard for clinical study of medical devices for human subjects, International Organization for Standardization (ISO) 14155:2011, and the International Conference on Harmonisation (ICH) guideline for GCP E6 (R2) as applicable for medical device.

Application to independent ethics committee

It is the responsibility of the Principal Investigator (PI) to obtain approval of the CSP amendment(s) from the independent ethics committee (IEC). The study shall not begin until the required favourable opinion from the IEC has been obtained. The PI shall file all correspondence with the IEC in the Investigator file and copies of IEC approvals shall be forwarded to the Sponsor. Any additional requirements imposed by the IEC shall be followed.

As the study product is CE-marked for the intended use, application for approval from competent authority (CA) is not required.

The collection, access to, processing, and transfer of protected health information or sensitive personal data shall be carried out in accordance with applicable rules and regulations (see further information in section 11).

2. Background Information

2.1 Indication and population description

Restylane Defyne is intended to augment the volume of facial tissues. It is recommended to be used for correction of severe wrinkles, or to redefine facial features. Depending on the area to be treated and the tissue support, the product should be injected in the mid to deep dermis, subcutis or supraperiostic zone. Lidocaine is added to the formulation to diminish the pain resulting from the injection during the treatment.

In this study, the investigational products will be used for stepwise treatment of the chin and nasolabial folds (NLF)/marionette lines (ML) within the approved indication.

Approximately 60 subjects, meeting all inclusion/exclusion criteria, will be enrolled to the study.

2.2 Study Product Profile

2.2.1 Investigational product description

Among the different materials used as raw materials in fillers, sodium hyaluronate, also denoted hyaluronic acid when found *in vivo* and hereinafter referred to as HA, is the most frequently used¹. HA is a naturally occurring polysaccharide found in all vertebrates and in some bacteria. HA based fillers typically exhibit better biocompatibility and fewer adverse reactions than fillers made from other materials^{1,2}.

The chemical structure of HA is very simple with repeating disaccharide units of glucuronic acid and N-acetylglucosamine. As the chemical structure of HA is identical in all species and tissues, it is non-allergenic.

Restylane Defyne is a sterile, biodegradable, transparent gel of non-animal cross-linked HA 20 mg/mL with the addition of lidocaine hydrochloride 3 mg/mL. The gel is supplied in a prefilled plastic syringe. The contents of the syringe are sterilized using moist heat. The syringe is packaged individually in a blister, with two 27G x ½" Ultra Thin Wall (UTW) needles. The needles have been sterilized using irradiation. Restylane Defyne was CE-marked 2010 with the previous name Emervel® Deep Lidocaine. Restylane Defyne is a product whose functional component, cross-linked HA, is obtained by using the

Doe id 05DF1910 Clinical Study Protocol 🚣 GALDERMA MA-42248

2.2.1.2 Clinical documentation

The first injectable OBT gel product was CE-marked in Europe in 2009. Several studies have been conducted to assess the safety and efficacy of OBT products in the treatment of e.g. cheeks, NLFs, and lips 6-10.

Study rationale and justification for design 2.3

This study aims to document the results of a stepwise treatment and determine if any of the two approaches to be used in this study, down-up and top-down, affects the studied endpoints. Results from the study will be the basis for future treatment guidelines used by aesthetic health care practitioners when injecting Restylane Defyne in the chin, NLF and ML.

Approximately 60 subjects (of which at least 20 males) will be enrolled and randomized into two groups with different treatment schedules. Comparison between the two groups will help to determine if the different treatment approaches affects the outcome, such as subject satisfaction.

Risks and benefits

After the injection of the study products, some common injection-related reactions might occur. These reactions include erythema, swelling, pain, itching, bruising or tenderness at the implant site. Typically, resolution is spontaneous within a few days after injection.

There is a risk that the subject will not gain the full aesthetic correction of the treated areas. There is also a risk for development of palpable HA lumps or displacement of the injected HA. Inflammation or infection has been reported in a few cases after treatment. There may be risk of bruising and/or damaging body structures such as nerves or blood vessels connected to the injection site, however these risks are minor.

Following facial aesthetic treatments isolated rare cases have been reported regarding ischemic events affecting the eye leading to visual loss, and the brain resulting in cerebral infarction. Detailed information on reported adverse events (AE) relevant for the study product is provided in the instructions for use (IFU).

Lidocaine can in rare cases give allergic reactions, and therefore subjects with known allergy or hypersensitivity to local anaesthetics should not be included in the study.

Given the anticipated low level of transient and acceptable AEs in connection with the injection, the risk-benefit assessment of the use of the study products for lower face augmentation offers a potential clinical benefit, such as subject rated improvement of attractiveness and satisfaction, at reasonable risk.

Objective(s) and Endpoint(s)

3.1 Objectives and endpoints

3.1.1 Effectiveness objectives and endpoints

Objective

Endpoint

and Treating Investigator assessment using the Global Aesthetic Improvement Scale at week 3, 6 and 9.

Objective

To evaluate naturalness of the treatment result

Endpoint

Assessed by and Treating Investigator using directed questions at week 3, 6 and 9.

Objective

To evaluate subject satisfaction treating chin versus treating NLF/ML, respectively, and in combination.

Endpoint

MA-42248.doc

Doc id 05DF1910 Clinical Study Protocol 🚣 GALDERMA MA-42248

Subject assessment using subject satisfaction questionnaire and at baseline, week 3, 6 and 9.

3.1.2 Safety objective and endpoints

Objective:

To evaluate AEs collected throughout the study

Endpoint

Incidence, intensity, duration and onset of AEs collected from injection of study product to patient withdrawal or end of study (visit 5).

Design of the Study

General outline

This is a 12-week, randomized, male-female and site stratified, evaluator-blinded, multicentre study to evaluate the effectiveness and safety of Restylane Defyne when using two different injection approaches, stepwise down-up vs. top-down, when treating the lower face.

Approximately 60 subjects requiring augmentation and correction therapy in the chin, NLFs and MLs fulfilling all eligibility criteria will be enrolled in the study. The subjects will be randomized to one of two treatment groups, the first treatment group will receive injections in the chin area at baseline and in the NLFs and MLs at the visit 3 (week 3), the second group will undergo the same treatment but in reverse order. The two groups are referred to as downup and top-down. Male-female stratification will be applied in the randomization and the aim is to randomize 10 male subjects to each group.

[figure not shown]
Doe id 05DF1910 Clinical Study Protocol 🚣 GALDERMA MA-42248

Six weeks after the second treatment, at visit 4, an optional touch-up will be administered to subjects that have not obtained optimal aesthetic improvement as agreed between subject and Investigator.

The subject will return to the clinic for a final follow-up visit (visit 5) 9 weeks after the first treatment.

All efficacy study assessments will be performed before treatment and safety will be followed by AE and device deficiency reporting throughout the study.

The Investigator will assess, Global Aesthetic Improvement Scale (GAIS), naturalness/ and safety. The subject assessments include, subject satisfaction questionnaire.

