4.6.1 Recording

Prior and concomitant therapies are to be recorded in the eCRF and reviewed, and updated if needed, at each visit.

Any new concomitant therapy or modification of an existing therapy may be linked to an AE. A corresponding AE form must be completed to account for the change in therapy, except in some cases such as therapy used for prophylaxis, dose modification for a chronic condition.

Doc id 05DF1910 Clinical Study Protocol ♣ GALDERMA MA-42248

Schedule of Events

Table 1. Schedule of events

	Visit 1	Visit 2	Visit 3	Visit 4	Visit 5
	Screening ¹	Baseline/ Day 1	Week 3	Week 6	Week 9
		(within 3 weeks after screening)	(21 ± 3 days from visit 2)	(42 ± 3 days from visit 2)	(63 ± 5 days from visit 2)
Informed Consent	X	(X) ²			
Demographic Data including, Fitzpatrick skin type, medical history & concurrent diseases, previous facial treatments/procedures	X	(X) ²			
Weight and height	X	(X) ²			X^3
Inclusion /Exclusion Criteria	X	X			
Concomitant Medication/ Procedures	X	X	X	X	X
Urine Pregnancy Test		X	X	X ⁴	
Photography 2D		X	X	X	X
Randomization		X			
Treatment ⁵		X	X	X ⁶	
Adverse Events ⁷		X	X	X	X
Investigator Assessment					
GAIS			X	X	X
Naturalness CCI around the chin.		X ⁸	X ⁸	X	X
Subject Assessment					

- The screening visit and baseline visit (visit 2) may be performed on the same day
- Screening visit assessments should be performed on the same day as the baseline visit if no separate screening visit has been 2) completed
- 3) Weight only
- If touch-up treatment is planned 4)
- Treatment to be performed after all assessments have been completed. 5)
- Optional touch-up injection
- AE reporting period starts at the baseline visit after randomization 7)
- Only applicable questions 8)
- 9)
- essments to be performed after end of study 10)
- 11)

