8.1.6 Follow-up of unresolved events ongoing at termination of the study

All serious as well as non-serious AEs with a causal relationship to the study product or treatment procedure and ongoing at study end, shall be followed up after the subject's participation in the study is over. Such events shall be followed-up after the last study visit until resolved, assessed as chronic or stable, or for three months. Final outcome after the end of the study shall be reported on AE follow up form.

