10.4 Safety analysis

Adverse events will be summarised in frequency tables by study product, containing number of subjects with no AEs, number of subjects with at least one AE, and number of events, subdivided by related/unrelated, serious/non-serious. All AEs will be summarised and listed by system organ class (SOC) and preferred term (PT) assigned using MedDRA. Furthermore, AEs will be summarised by causality, and both related and unrelated events will be summarised separately by maximum intensity. For related AEs, i.e. AEs judged by the Investigator or Sponsor to be related to the study product and/or study product injection procedure, the number of days to onset and the duration of the event will be summarised by PT.

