10.5 Handling of missing data

Study data will be presented based on observed cases, i.e. no imputation of missing values will be performed.

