Vascular compromise may occur due to an inadvertent intravascular injection or as a result of vascular compression associated with implantation of any injectable product. This may manifest as ischemia or necrosis at the implant site or in the area supplied by the blood vessels affected; or rarely as ischemic events in other organs due to embolisation. Following facial aesthetic treatments isolated rare cases have been reported regarding ischemic events affecting the eye leading to visual loss, and the brain resulting in cerebral infarction. After injections of the nose ischemia/necrosis may occur, especially in patients who had prior rhinoplasty.

Symptoms of inflammation at the implant site commencing either shortly after injection or after a delay of up to several weeks have been reported. In case of unexplained inflammatory reactions infections should be excluded and treated if necessary since inadequately treated infections may progress into complications such as abscess formation. Treatment using only oral corticosteroids without concurrent antibiotic treatment is not recommended. In case of persistent or recurrent inflammatory symptoms, consider removal of the product by aspiration/drainage, extrusion or enzymatic degradation (use of hyaluronidase has been described in scientific publications). Before any removal procedure is performed, the swelling may be reduced by using e.g. NSAID for 2-7 days or a short course of corticosteroids for less than 7 days, in order to more easily palpate any remaining product.

For patients who have experienced medically important adverse events, a decision for retreatment should take into consideration the cause and severity of previous reactions.

For reporting adverse events contact your local Galderma representative or distributor for this product.

IX. PERFORMANCE

In a randomized controlled multicenter study with Restylane Defyne for correction of moderate to severe nasolabial folds, 69.8% of subjects maintained a clinically significant improvement at 48 weeks after treatment.

X. TREATMENT PROCEDURE

Inform the patient about the precautions to be taken, the expected result and the possible adverse events.

It is important to use a sterile, appropriate needle or blunt cannula. Suitable needles (27G x ½" Ultra thin wall) are supplied with the syringe in the blister pack. As an alternative, a blunt thin walled cannula with a recommended size of 27G can be used.

Assembling the needle/cannula and syringe:

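### The AE duration endpoint stops at visit 5 with no rule for related events still unresolved then, so persistent reactions would be summarised as shorter than they are

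*Combined protocol and SAP*

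**What the plan says.** Section 3.1.2 gives the safety endpoint as "Incidence, intensity, duration and onset of AEs collected from injection of study product to patient withdrawal or end of study (visit 5"). Section 8.1.4 likewise ends routine AE reporting at the last scheduled visit.

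Table 1 (section 4.7) counts every visit from visit 2: the second injection at "21 ± 3 days from visit 2", the optional touch-up at "42 ± 3 days from visit 2", and the final visit at "63 ± 5 days from visit 2".

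For related AEs, section 10.4 says that "the number of days to onset and the duration of the event will be summarised by PT". It sets no data cut-off and gives no rule for an event without a stop date. Section 10.5 presents observed cases and adds that "no imputation of missing values will be performed".

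Section 8.1.6 deals with related AEs ongoing at study end: "Such events shall be followed-up after the last study visit until resolved, assessed as chronic or stable, or for three months". The final outcome goes on an AE follow-up form. Section 8.1.7 requires related AEs that start after the last visit to be reported and followed, but only those the Investigator becomes aware of. Neither section says whether its data enter the tables of section 10.4.

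The Instructions for Use in Appendix 3 state that symptoms of inflammation at the implant site "commencing either shortly after injection or after a delay of up to several weeks have been reported". They also list nodules, induration and mass among reported events, and the protocol's risk section names palpable lumps.

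**The concern.** An event still present at visit 5 has no stop date, so its duration cannot be computed from data up to that visit. If it is left out of the duration summary, the omission depends on the outcome: the longer an event lasts, the more likely it is to be left out. The summary then describes the events that happened to resolve in time, and it is biased short.

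The window is narrowest for events that begin at the touch-up, which is also the last exposure. Persistent and delayed reactions are the ones for which a reader would consult a duration table, and section 2.3 says the results will be the basis for treatment guidelines. The missing stop dates are mostly obtainable, because section 8.1.6 already requires follow-up of these events. The gap is that nothing brings that information into the analysis.

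**Working it through.** The plan gives no figure for observation after the last injection and no calculated sample size, so there is no stated number to reproduce.

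**Observation windows.** From Table 1, in days from visit 2:

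- Visit 3: 21 ± 3, so day 18 to 24.
- Visit 4: 42 ± 3, so day 39 to 45.
- Visit 5: 63 ± 5, so day 58 to 68.

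The shortest interval is the earliest visit 5 minus the latest injection visit. The longest is the latest visit 5 minus the earliest injection visit.

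- After a touch-up: 58 − 45 = 13 to 68 − 39 = 29 days, nominally 63 − 42 = 21.
- After the second injection: 58 − 24 = 34 to 68 − 18 = 50 days, nominally 63 − 21 = 42.
- After the first injection: 58 to 68 days.

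**Effect of leaving out unresolved events.** The documents give no distribution of durations. As an assumption, take exponential durations with true mean m, all starting at the injection, and a window of T days.

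- Share unresolved at visit 5: exp(−T/m).
- Mean duration among resolved events: m − T·exp(−T/m) / (1 − exp(−T/m)).

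For T = 21, the nominal interval after a touch-up:

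| Assumed true mean (days) | Unresolved | Mean of resolved events (days) |
|---|---|---|
| 5 | 1.5% | 4.7 |
| 7 | 5% | 5.9 |
| 15 | 25% | 8.1 |
| 30 | 50% | 9.3 |
| 60 | 70% | 9.9 |

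Worked line for m = 30: exp(−21/30) = 0.497, and 30 − 21 × 0.497 / 0.503 = 9.3.

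For m = 30 across the permitted range:

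- T = 13: 65% unresolved, resolved mean 6.0 days.
- T = 29: 38% unresolved, resolved mean 12.2 days.
- T = 42 (nominal, second injection without a touch-up): 25% unresolved, resolved mean 16.3 days.

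For m = 7 at the shortest window, T = 13: 16% unresolved, resolved mean 4.6 days.

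True means from 15 to 60 days would therefore be reported as roughly 8 to 10 days at the nominal window, and the reported figure depends heavily on when visit 5 falls. The protocol's risk section describes common injection reactions as typically resolving within a few days. Section 6.5.3 and the Instructions for Use say about a week. For those reactions the nominal bias is about one day or less (7 − 5.9 = 1.1; 5 − 4.7 = 0.3).

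**What the follow-up already required would recover.** Taking three months as 90 to 91 days, a related AE ongoing at visit 5 could be observed to 13 + 90 = 103 up to 29 + 91 = 120 days after a touch-up. At the nominal 21 + 90 = 111 days, and under the same assumption, the unresolved share falls to below 0.1%, 2.5% and 16% for true means of 15, 30 and 60 days. Some events will still be open, or classed as chronic or stable, so a rule for unresolved events is still needed.

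**The case against.** The best counter-argument is that the loss of long events is an inference. Section 3.1.2 limits the AEs collected up to visit 5, which can be read as limiting onset only. Section 8.1.6 puts the final outcome on a form, section 10.4 does not exclude that form, and a stop date obtained in follow-up is observed, not imputed. This reading is possible, but no sentence adopts it. It also leaves open how to handle an event unresolved when follow-up ends. The wording permits two different tables, so it needs to be settled.

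The size argument also has force. Means of 15 to 60 days have no source in the documents, and for the common reactions the effect is small. The 13 to 29 days apply only to subjects who have a touch-up and to events starting then. Kaplan-Meier estimates by preferred term in about 60 subjects will often rest on few events. These points limit the finding without removing it.

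A reader might also infer three stronger things, none of which the documents support:

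- **That AE reporting as a whole is cut off.** An event that starts by visit 5 still counts for incidence, intensity and onset, is listed, and can be coded as not recovered. Only duration is affected.
- **That late-onset events are lost altogether.** Section 8.1.7 requires those the Investigator learns of to be reported and followed. They fall outside the endpoint, and their capture is passive, so it is incomplete.
- **That the two randomised groups are watched for different times.** Both share the same schedule and touch-up rule, visit 5 is timed from visit 2 for everyone, and nothing suggests different touch-up use. Observation after the last injection does differ by touch-up status (nominally 21 against 42 days), but that is not a difference between the groups.

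**Conclusion.** The concern holds for the duration of related AEs. As written, events unresolved at visit 5 have no stop date and no handling rule, so they leave the duration summary, which is then biased short for persistent reactions. The window arithmetic is exact. The size of the bias rests on assumed exponential durations with onset at the touch-up: at 21 days, from about 5% unresolved and a one-day bias with a 7-day mean, to about 50% unresolved and a reported 9.3 days with a 30-day mean. How many persistent events will occur cannot be known from the documents. The change is worth making because the data are already to be collected and the remedy is mainly wording.

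**What to change.** 1. In sections 3.1.2 and 10.4, state that the duration of related AEs with onset by visit 5 uses the stop date or final outcome from the AE follow-up form of section 8.1.6.
2. In section 10.4, show the number of related AEs still ongoing beside each duration summary and treat them as censored. Give a Kaplan-Meier median where event numbers allow, and otherwise the count and a listing.
3. List related AEs with onset after visit 5, reported under section 8.1.7, separately. Note that their ascertainment is passive and incomplete, and do not pool them with events found by questioning at visits.
4. Leave the timing of visit 5 alone. Moving it would shift the week-9 efficacy window and would not remove the difference in observation between subjects with and without a touch-up.
5. Reconcile the general outline of the design with Table 1. The outline places visit 4 six weeks after the second treatment. Taken literally that is day 18 + 42 = 60 to 24 + 42 = 66, which is anywhere from 8 days before to 8 days after visit 5. Table 1 gives 42 ± 3 days from visit 2. The windows above use Table 1.

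Cost: some duration tables close, or are updated, up to three months after the last visit, and reported durations become less favourable. No new data collection is needed.
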